Identification of families (i.e., households): We will group families using one of two possible methods. First, LADHS has an identifier that ties family members together. It is called the "Family Budget Unit." We will explore this method. If it does not work, we will use another method that we have utilized successfully in the UCLA-based study from which this study is derived. We will assume that people living in the same address belong to the same family. As a secondary measure, we use a telephone number as a linking number (i.e., if two people have the same telephone number, we assume they are from the same household).

We will randomly allocate families to one of the study arms shown above and send family members the allocated text message. All family members will therefore receive the same text message. This is meant to reduce confusion among patients. For the analysis, we will randomly select one index patient per household for analysis. This follows Cochrane criteria for being included in meta-analyses. We will attempt to affiliate index patients with practices, and randomize patients (families) within these practices.

Assignment to the intervention: All patients will be eligible for the intervention. There are no specific inclusion or exclusion criteria. Since we will send up to 3 text messages in October-December 2022, we will search the EHR for whether or not the patient received an influenza vaccination this season. If yes, the patients will be dropped form the denominator of patients needing a text message reminder. We will search the EHR prior to each of the text message rounds.

Review of medical records is needed in order to obtain the information about (a) influenza vaccination dates this upcoming season, and (b) address (in order to group patients into households as described above. We will review the EHR prior to each round of text messages to see if patients had received an influenza this season.

Description of the Interventions:

Text messages will begin to be sent in early October. We will randomly spread out the calls throughout the day and week in order to minimize unnecessary overload for the call center when patients text back a "1" response that they would like a call or text message to help them. We can do this by randomizing patients into batches so that there is no systematic time-of-day or day-of-week for any patients. We will send up to 3 reminders this upcoming season.

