All study data, including CAIR2 data and DHS EMR and administrative data will be prepared by the DHS-CTSI Informatics Core in accordance with the DHS Research Oversight Board policy. [name] will submit all data requests to the DHS helpdesk, which includes verification of procedural compliance with IRB and ROB approval screening for DHS-based research. Only HIPAA-limited or deidentified data sets will be transferred for analysis purposes; compliance with the DHS secure data transfer process to UCLA and/or USC will be managed by [name] as DHS Principal Investigator. Any links between identified data and deidentified data will be stored only on DHS premises. Patient contact lists and personalized data elements will be exclusively maintained on premises by the Informatics Core, responsible for implementing the patient assignment and personalization templates.

Statistical Analysis of Randomized Trial. We will perform separate evaluations of the impact of the text enhancements (callback and bidirectional texting) on the one hand, and transportation messaging on the other hand. For both analyses, we will use multivariable log-binomial regression models with vaccination status at the end of the campaign as the outcome variable. Regressions will include indicators for each intervention as fixed effects, with the standard text condition as the reference group, and potentially clinic random effects, depending on retrospective analysis results. Models will also adjust for patient age, gender, race/ethnicity, insurance, and whether the patient was vaccinated in at least one of the prior two flu seasons. Secondary analysis will include subgroup interactions with intervention indicators to assess heterogeneity of treatment effects. In exploratory analyses, we will investigate interactions between interventions, questions related to modality of message delivery, as well as whether encounter type, click rates on messages, and distance to the health care facility from the home address affect influenza vaccination rates.

In addition, we will evaluate the loss to follow-through rates (scheduling an appointment, but did not complete the appointment) by patient demographics, as distance to the health care facility from the home address).

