For the evaluation of text enhancements, we will perform a 3-fold Bonferroni correction accounting for pairwise comparison of intervention arms, using a two-sided significance level of 0.017. For the evaluation of transportation messaging, we will use a two-sided significance level of 0.05. All analyses will be intention-to-treat, and will be performed using SAS v. 9.4 (SAS Institute Inc., Cary, NC).

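### Families are to be randomised within practices, but practice is optional in both analysis models; always including it would cost almost nothing and recover a little precision

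*Combined protocol and SAP*

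**What the plan says.** The part of the protocol on identifying families makes the family the unit of allocation: "We will randomly allocate families to one of the study arms shown above and send family members the allocated text message". It then adds: "We will attempt to affiliate index patients with practices, and randomize patients (families) within these practices". One index patient per household, chosen at random, enters the analysis.

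Under Statistical Analysis of Randomized Trial, the text-enhancement evaluation and the transportation evaluation share one model form: "we will use multivariable log-binomial regression models with vaccination status at the end of the campaign as the outcome variable". The models contain the arm indicators, with standard texts as reference, and "potentially clinic random effects, depending on retrospective analysis results". The covariate list begins "Models will also adjust for patient age, gender, race/ethnicity, insurance" and ends with prior influenza vaccination; it contains neither clinic nor practice. The text-enhancement comparisons are tested "using a two-sided significance level of 0.017"; for transportation, "we will use a two-sided significance level of 0.05". The section closes with "All analyses will be intention-to-treat".

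The documents do not say what the retrospective analysis is, or what result would bring clinic into the model. They also do not say whether allocation is blocked within practice, or whether the allocation ratio is the same in every practice.

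**The concern.** A factor used to structure the randomisation normally belongs in the analysis because of the design. Here its inclusion turns on an undefined retrospective result that has no link to how families were allocated. An analyst could leave practice out of both planned evaluations without departing from the plan.

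What is at stake is mainly efficiency. If allocation is balanced within practices, differences between practices cancel from the arm comparison, yet they stay in the residual variance of a model that ignores practice. The reported standard error then overstates the true one. If allocation is not balanced, practice differences add avoidable noise to the estimate. Any loss matters most for the small arms (3,050 with transportation information, and 7,000 in each enhanced arm), since they set the precision of every comparison. An open choice about the primary model is also better closed before outcome data are seen.

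**Working it through.** **No figure to reproduce.** The documents give no power, effect size, baseline vaccination rate, number of clinics or between-clinic variance.

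**Inputs from the documents.** Arm sizes 232,950, 3,050, 7,000 and 7,000; two-sided levels 0.05 and 0.017.

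**Assumed inputs.** Vaccination rate p = 0.30, so total variance p(1−p) = 0.30 × 0.70 = 0.21. Between-clinic SD s of 0.03 to 0.10 on the risk scale.

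**Step 1: standard error before covariates.** The within-clinic variance is 0.21 − s². The SE with practice, relative to the model-based SE without it, is r = √(1 − s²/0.21). For s = 0.10: 0.01/0.21 = 0.0476, r = √0.9524 = 0.976, so the SE is 2.4% smaller with practice.

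**Step 2: level and power if allocation is balanced within practice at a constant ratio.** The estimate has the same true spread with and without practice; only the reported SE differs. With z the critical value (1.960 or 2.387):
- true level without practice = 2[1 − Φ(z/r)]
- power without practice, where it is 80% with practice = 1 − Φ(z/r − (z + 0.842))

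| Clinic SD | SE smaller with practice | True level, nominal 0.05 | True level, nominal 0.017 | Power at 0.05 | Power at 0.017 |
|---|---|---|---|---|---|
| 0.03 | 0.2% | 0.0495 | 0.0168 | 79.9% | 79.9% |
| 0.05 | 0.6% | 0.0486 | 0.0163 | 79.7% | 79.6% |
| 0.08 | 1.5% | 0.0465 | 0.0154 | 79.1% | 78.9% |
| 0.10 | 2.4% | 0.0446 | 0.0145 | 78.6% | 78.3% |

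**Step 3: after covariates.** Let the covariates absorb a share f of the between-clinic variance and R of the within-clinic variance. The SE reduction is 1 − √(w/(w+b)), with b = s²(1−f) and w = (0.21−s²)(1−R). With R = 0.2:

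| Clinic SD | f = 0 | f = 0.5 | f = 0.75 | f = 0.9 |
|---|---|---|---|---|
| 0.03 | 0.3% | 0.1% | 0.1% | 0.0% |
| 0.05 | 0.7% | 0.4% | 0.2% | 0.1% |
| 0.08 | 1.9% | 1.0% | 0.5% | 0.2% |
| 0.10 | 3.0% | 1.5% | 0.8% | 0.3% |

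**Step 4: simulation under balanced allocation.** This used 25 assumed practices, no treatment effect, one prior-vaccination covariate (assumed uptake 55% against 15%) and 40,000 replicates. A Mantel-Haenszel risk ratio stood in for the log-binomial model.
- 3,050 against 232,950 at 0.05, f = 0, SD 0.05 and 0.10: level 0.049 and 0.045 without practice, 0.050 and 0.049 with it. The empirical spread of the log risk ratio was the same either way (0.0244 at SD 0.10).
- 7,000 against 7,000 at 0.017, f = 0.5, same SDs: level 0.0167 and 0.0152 without practice, 0.0172 and 0.0169 with it.

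**Step 5: other allocation schemes.** These simulations also assumed 25 clinics, with vaccination rates of 20% or 40%.
- *Simple allocation inside practices.* The reported SE without practice was correct (reported-to-true ratio 0.99 to 1.01), so the levels in the Step 2 table do not apply. The loss is precision only: power is Φ(r(z + 0.842) − z). For SD 0.10 at 0.05 this is Φ(0.976 × 2.802 − 1.960), about 78%, where practice in the model would give 80%.
- *Ratio differing between practices* (illustrative log-SD 0.3). Results were erratic. In one case (3,050 against 232,950, rate 20%, 2% of outcome variance between clinics, nominal 0.05) the log risk ratio was biased by 0.046 and the test rejected 26% of the time, against 5.0% when stratified by clinic. Other cases stayed near nominal, for example 0.046 and 0.047.

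**The case against.** The strongest reply is that the consequence is uncertain and small. The protocol speaks only of attempting to randomise within practices and describes no blocking. If allocation inside practices is simple, the standard error without practice is correct and no test runs below its level. This stands, and the point is worded accordingly.

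A second reply is that the retrospective rule may already work. On a natural reading, clinic enters when past data show that it matters, so it would be left out mainly where its variance is small. At clinic SDs of 3 to 5 points that costs only about 0.2 to 0.6% of the SE before covariates. This is fair and pulls the likely loss towards the low end. It does not close the gap, because neither the retrospective analysis nor its threshold is defined.

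A third reply is that very large clinic differences are implausible. An SD of 15 points around 30% would span roughly 0 to 60% at two SDs either side. That is accepted, and the range used here stops at 10 points.

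Three stronger readings are tempting and not supported:
- *That leaving clinic out inflates type I error, as in a cluster trial.* Families, not practices, are randomised, and one index patient per household is analysed. Practice is a stratum, not a randomised cluster.
- *That the tests will definitely run below their stated levels.* That requires balanced allocation within practice, which is not stated.
- *That the planned estimate is biased.* That requires allocation ratios that vary by practice, and nothing in the documents suggests they do.

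**Conclusion.** The point holds as a small, nearly free improvement in the primary models, not as a threat to validity. The text leaves room to omit a randomisation stratum from both evaluations, on a criterion unrelated to the randomisation. Under balanced, constant-ratio allocation the cost is a slightly conservative test; under simple allocation it is a slightly less precise estimate. Only under practice-specific ratios, which the documents neither state nor rule out, could it be bias.

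The likely gain in SE is a fraction of a per cent to about 1.5% if the covariates absorb half of the between-clinic variance, and about 2.4% at most before covariates. This rests on an assumed 30% rate and clinic SDs of 3 to 10 points, neither of which is in the documents. Including practice is the right remedy under all three allocation schemes, so the recommendation does not depend on the unstated details. Minor priority.

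**What to change.** Replace the conditional clause under Statistical Analysis of Randomized Trial with a commitment along these lines: wherever randomisation was carried out within practices, the practice used at randomisation is included in both log-binomial models as the clinic random effect, whatever the retrospective analysis shows.

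Two supporting details belong with it:
- Index patients who could not be affiliated with a practice form their own category, so none drops out of the intention-to-treat analysis.
- A fallback is named in advance in case the log-binomial model does not converge, for example modified Poisson regression with robust variance, the same covariates and practice as a fixed effect.

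Keep one index patient per household as the primary analysis.

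The cost is two or three sentences in the SAP, one model term that the plan already names, and carrying the randomisation practice in the analysis file. The design, data collection and sample size do not change. The one practical risk is convergence with more terms in the model, which the fallback covers.
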